Statistical analysis plan. All of the analyses will be performed with SAS/STATv14.1. Data will be examined for distributional normality and outliers prior to any analyses. Descriptive statistics will be generated for all variables of interest included in the analysis, overall, and by intervention assignment. Univariate comparisons will consist of *t*-tests and ANOVA, and of chi-square and other non-parametric tests, if needed, for continuous and categorical variables, respectively. Randomization validity will be assessed by comparing intervention arms on baseline measures using *t*-test, chi-square test, ANOVA, and other appropriate tests. If imbalances are found, adjusting the between-group analyses for potential confounders will be considered. Primary analyses will be intention-to-treat, without regard to intervention adherence. Multivariable linear ANCOVA regression models will be used for continuous outcomes accounting for clustering effect within groups, to model and compare the PILI DPP-LI to the WORD DPP-LI (Aim 1). Using these models, treatment effects will be estimated and tested by comparing change in group-specific means at the post-intervention assessment, conservatively adjusting for baseline differences (which should be minimal by virtue of randomization) and taking in account intracluster correlation by assuming compound symmetry covariance structure.

The hypothesis is that participants randomized to the PILI DPP-LI will show a significantly higher percentage of weight loss compared to those randomized to the WORD DPP-LI. The main independent variable of interest is intervention assignment (PILI DPP-LI vs. WORD DPP-LI) and the primary outcome is percent body weight loss from pre- to post-intervention

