assessment. Measures of weight will be obtained at multiple points during the study (pre-intervention, post-intervention, and 12-months post-intervention), and both post-intervention and 12-months (six months post-initiation) will be modeled, but in separate models. General linear and mixed ANCOVA regression models for continuous measures with clustering will be utilized, with treatment effect estimated as the distance between the fitted group-specific means at the post-intervention assessment, while adjusting for the fitted distance between them at baseline, conservatively. In addition, an adjustment will be made within the model for demographic factors and other covariates listed above. In order to model the outcome at the 12-month time point, a similar model to the one described above will be applied with repeated measures, and incorporate intervention, time, and their interaction effect, while adjusting for the same covariates as in the first model. This will allow examination and test weight change trajectories over time for both groups. Secondary outcome measures that are continuous in nature, such as HbA1c, will also be modeled using the same approach used to test the primary outcome (a general linear mixed model). Secondary outcomes that are discrete will be modeled using logistic regression or generalized estimating equations (GEE) for repeated binary measures accounting for the correlation within groups.

Additional analysis will be done to: 1) determine if aspects of participants' built environment as measured by Google StreetView influence effectiveness of the project's intervention, 2) determine if aspects of the food environment based on Business Analyst in ArcGIS influence effectiveness of the project's intervention.

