Sensitivity analyses to determine the impact of key assumptions. We will examine the distributional assumptions for our outcome measures, which may prompt transformations if justified. We will also compare the results of parametric and non-parametric univariate tests (for instance Wilcoxon test, Kolmogorov-Smirnov test, or Fisher's Exact test, respectively) as a sensitivity step to confirm the inferences. In a case where distributional assumptions are not met, non-parametric tests will be applied. While we will track and analyze the effect of dosage (number of sessions completed), we will use an intention-to-treat analysis. To account for missing data we will compare imputation methods under several assumed missing data mechanisms, missing completely at random (MCAR), missing at random (MAR), and missing not at random (MNAR), in order to determine which underlying mechanism best fits our data.

Plans to address missing data. The study team will minimize missing data by using highly qualified staff to systematically collect data from all participants. Furthermore, we will use REDCap to monitor the occurrence of missing data during field collection. REDCap has a standard missing data report to facilitate the identification of missing data fields, which allows for continuous data quality monitoring so that missing data can be immediately collected. If a participant drops out, the study team will document why the drop out occurred. The study team will continue to collect information on all outcomes from participants, unless consent is withdrawn. Given recent advances in handling missing data in longitudinal studies, we have several reasonable approaches that we will apply and compare. We will compare the results of the analysis using three approaches as a comprehensive sensitivity check: 1) use a random effects model in SAS PROC MIXED (or weighted GEE for discrete outcomes) that makes use of all available data when assuming observations are missing completely at random (MCAR); 2)

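### The non-parametric fallback and confirmatory check name only tests that ignore church clustering, and the plan does not say whether the fallback can replace the clustered primary model

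*Combined protocol and SAP*

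**What the plan says.** All references are to the combined protocol and SAP.

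- *Randomized participant assignment*: churches are randomised 1:1, within blocks formed by region and approximate adult membership. All groups within a church go to the same arm.
- *Power, sample size, and detectable effects*: 16 churches per arm with 12 participants each, ICC 0.01, two-sided 0.05 level.
- *Statistical analysis plan*: the primary comparison is a baseline-adjusted model "taking in account intracluster correlation by assuming compound symmetry covariance structure"; later in the section, "General linear and mixed ANCOVA regression models for continuous measures with clustering will be utilized". Normality and outliers are examined before any analysis. Univariate comparisons use t-tests and ANOVA, with chi-square and "other non-parametric tests, if needed, for continuous and categorical variables, respectively".
- Same section, on covariates: "an adjustment will be made within the model for demographic factors and other covariates listed above". Neither region nor church size is named as a model term.
- *Sensitivity analyses to determine the impact of key assumptions*: the distributional checks are ones "which may prompt transformations if justified". Parametric and non-parametric univariate tests are then compared ("for instance Wilcoxon test, Kolmogorov-Smirnov test", or Fisher's Exact) "as a sensitivity step to confirm the inferences". The fallback follows: "In a case where distributional assumptions are not met, non-parametric tests will be applied".

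No section gives a cluster-level, cluster-adjusted or permutation version of these tests.

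**The concern.** The plan takes care over within-church correlation in its models and is silent about it for the tests that may replace or support them. Two readings of the sensitivity section are open.

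1. **The fallback can replace the primary model.** A data-dependent normality check, with no stated trigger, could then move the primary inference to a test that ignores the randomised unit and does not hold the 5% level.
2. **The fallback covers only the univariate comparisons.** The primary model is then untouched. But the t-test and its rank counterpart both ignore clustering, so their agreement says nothing about whether the clustered inference is sound, although confirming inferences is the step's stated purpose.

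A smaller, separate matter is that the factors used to block the randomisation are not named in the primary model.

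**Working it through.** **Inputs from the plan.** k = 16 churches per arm, m = 12 per church, ICC 0.01, difference 2.5 kg, SD 7, two-sided alpha 0.05, stated power 91%.

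**Reproducing the plan's figure.** Design effect = 1 + (12 - 1) x 0.01 = 1.11. Effective n per arm = 192 / 1.11 = 172.97. Power is 0.913 by the normal approximation, 0.912 by noncentral t on 382 df and 0.895 on 30 df. The stated 91% reproduces, so the plan's own power figure already allows for clustering.

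**Type I error of an unclustered t-test.** Error = 2 x (1 - Phi(1.96 / sqrt(DEFF))).
- ICC 0.01: DEFF 1.11, error 6.3%.
- ICC 0.05 (assumed): DEFF = 1 + 11 x 0.05 = 1.55, error 11.5%.

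**Type I error of an unclustered Wilcoxon test.** For normal data the ICC on the rank scale is (6/pi) x asin(ICC/2).
- ICC 0.01: rank ICC 0.0095, DEFF = 1 + 11 x 0.0095 = 1.105, error 6.2%.
- ICC 0.05 (assumed): rank ICC 0.0478, DEFF 1.525, error 11.2%.

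**Null simulations**, 32 churches of 12. The Wilcoxon ranges cover several independent runs of 20,000 to 40,000 trials; the Kolmogorov-Smirnov runs had 4,000 to 20,000. The t4 column assumes heavy-tailed errors (t on 4 df).

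| Test | ICC | Normal | t4 |
|---|---|---|---|
| Wilcoxon | 0 (check) | 4.9-5.1% | 5.0-5.3% |
| Wilcoxon | 0.01 (plan) | 6.0-6.4% | 6.7-7.1% |
| Wilcoxon | 0.05 (assumed) | 11.2-11.7% | 13.5-14.0% |
| Kolmogorov-Smirnov | 0.01 (plan) | 5.2% | 5.7% |
| Kolmogorov-Smirnov | 0.05 (assumed) | 8.9-9.0% | 11.4% |

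Kolmogorov-Smirnov looks better partly because it is conservative to begin with: 4.1% at ICC 0 with normal data. A t-test on church means, a simple clustered analysis, stayed at 4.8-5.2% throughout, including with t4 tails. Heavy tails of that kind therefore do not by themselves force a departure from clustered, mean-based inference.

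**Cluster-respecting rank test.** A church-level permutation test on ranks within 8 blocks of 4 churches held 4.7-5.3%. Its power for 2.5 kg at ICC 0.01 was 87.8%, against 89.6% for the church-mean t-test, with normal data (about 2 points lower), and 95.3% against 88.9% with t4 tails. The comparator is the church-mean t-test on 30 df, not the plan's covariate-adjusted mixed model.

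**Blocking factors** (assumed layouts of 4 x 2 or 4 x 4 region-by-size cells), at ICC 0.01.
- If the blocks explain half the between-church variance (assumed), type I error without them is 4.5-4.7%, which is conservative. Main effects raise power from 90.2-90.3% to 90.5-90.7%, about +0.3 to +0.4 points.
- If they explain nothing, power starts at 89.5% (30 df). Main effects cost 0.3 points (26 df) or 0.5 (24 df); 16 saturated cells cost 2.2 (15 df).
- At an assumed ICC of 0.05 with half explained, power rises from 81.1-81.9% to 85.1-85.4%.

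**The case against.** The strongest reply is that nothing here shows a planned unclustered primary test. The fallback sentence names no test. The examples stand in the sentence before it and are introduced as instances, so a clustered version is unspecified rather than excluded. Transformations are offered too, the sentence sits under sensitivity analyses, and the analysis section commits the primary outcome to models that allow for clustering. All of that stands: replacement of the primary model is a possible reading, not an established one.

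A reader might also infer that the Wilcoxon check is set against the mixed model and leans towards false agreement. Under the null at ICC 0.01 with t4 tails, Wilcoxon alone is significant in 3.4% of trials and a church-mean t-test alone in 1.5%. The text does not support that use, because it compares univariate tests with univariate tests. For Wilcoxon against the unclustered t-test the split is about 2.5-2.6% against 2.1-2.2%, nearly even. Part of the 3.4% is ordinary disagreement between two statistics: with no clustering at all the split is 2.2% against 2.1%.

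Third, the inflation is small at the only ICC in the documents. Wilcoxon errors as high as 16.4% can be produced, but only by combining an assumed ICC of 0.05, assumed t4 tails and an assumed spread of church sizes (4 to 27, mean 12). The plan expects some churches above 20 participants but gives no size distribution and no trigger for the fallback.

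What survives is that the univariate wording and every named example point to tests that ignore clustering, and nothing limits where the fallback applies.

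**Conclusion.** The sensitivity section needs clarifying and correcting. If the fallback replaces the primary model, the nominal 5% becomes about 6-7% for Wilcoxon and 5-6% for Kolmogorov-Smirnov at ICC 0.01; the upper ends assume t4 tails. The Wilcoxon figure becomes about 11-14% only if the ICC were 0.05, which is an assumption. If the fallback covers only univariate comparisons, the clustered primary result keeps its error rate, but the check pairs two tests that each run at about 6-7% at ICC 0.01, so their agreement is not confirmation. The figures assume equal churches of 12 and normally distributed church effects.

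The missing block terms are a minor precision point. A reader might infer that leaving them out threatens validity; it does not, since omission creates no false positives and adding them is roughly neutral at ICC 0.01. Nor can it be said that they are definitely excluded: the covariate sentence points back to a list that the analysis section does not contain.

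**What to change.** In *Sensitivity analyses to determine the impact of key assumptions*:

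- State that the clustered mixed model remains the primary analysis whatever the normality checks show.
- Require any fallback or confirmatory analysis to respect clustering. The preferred option is cluster-robust inference with a small-sample correction from the same model. It yields an effect and standard error, which is what the planned PROC MIANALYZE step combines over imputations. The alternative is a church-level rank or permutation test within randomisation blocks. That test supplies no such pair directly, so its rule for pooling over imputations must be written down.
- Label ordinary Wilcoxon, Kolmogorov-Smirnov and Fisher's Exact tests, and the unclustered t-tests beside them, as descriptive.

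Separately, in *Statistical analysis plan*, name region and church-size category as main effects in the primary model whatever the baseline comparisons show. Collapse sparse categories rather than fitting a term for every block.

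The cost is SAP wording and a little programming. No new data are needed, since the blocking factors are already required for randomisation. The church-level rank test gives up about 2 points of power if data are normal. Block main effects cost about 0.3 to 0.5 points at ICC 0.01 if uninformative.

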Power, sample size, and detectable effects. All of the power calculations were conducted with PASS12.³¹ The primary objective of the analysis is to estimate the effect of the PILI DPP-LI relative to the effect of the WORD DPP-LI with respect to the percentage of weight loss from pre- to post-intervention. Based on prior PILI DPP-LI research,²¹ it is hypothesized that the adapted intervention will result in 2.5kg weight loss (SD=7) larger than the WORD DPP-LI (this is ~4% body weight loss), which reflects a medium effect size of 0.36.³² Using the randomized clustered design, it is estimated that a sample size of 32 churches (16 clusters per arm with 12 individuals per cluster) would total N=384. This achieves 91% power to detect a difference of 2.5kg between the group means when the standard deviation is 7 (ES=0.35) and the intra-cluster correlation is 0.01 using a two-sided *t*-test with a significance level of 0.05, or 80% to detect smaller effects (ES=0.31) if observed. It is planned to impute missing data (see below), therefore all randomized participants will be included in the analysis according to an intention-to-treat protocol.

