perform multiple imputations (N=25) in SAS PROC MI when assuming observations are missing at random (MAR); and 3) perform pattern-mixture model imputations in SAS PROC MI when assuming observations are missing not at random (MNAR). To address this potential source of inferential error, we will use monotone regression-based, multiple random imputations of the outcomes. These imputations will help minimize loss of power resulting from attrition. We will use demographic covariates and prior weight measurements that are available in this predictive model. The analysis will then be carried out in multiple data sets, and the results combined using standard methods in SAS PROC MIANALYZE to produce summary effect and standard error estimates that incorporate the imputation error.³³⁻³⁴

Plans to address heterogeneity of treatment effect. Potential differential effects of the PILI DPP-LI among subgroups will be evaluated to determine its effectiveness in specific population segments. This will be done by testing two-way interactions between intervention assignment and covariates of interest. These include sex, age, education, insurance status, and marital status. Bonferroni correction will be applied to control p-values for multiple comparisons. For these exploratory comparisons, we will report all relevant subgroup outcomes analyzed.

Ethical Considerations. This study will be conducted in accordance with all applicable government regulations and University of Arkansas for Medical Sciences research policies and procedures. This protocol and any amendments will be submitted and approved by the UAMS Institutional Review Board (IRB) to conduct the study.

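### Comparing methods cannot tell MAR from MNAR, the assumption behind the primary imputation is not fixed, and the named imputation predictors do not include arm

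*Combined protocol and SAP*

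**What the plan says.** The combined protocol and SAP treats missing outcomes in four places.

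- **Power, sample size, and detectable effects:** "It is planned to impute missing data (see below), therefore all randomized participants will be included in the analysis". No missing fraction is given.
- **Statistical analysis plan:** "Primary analyses will be intention-to-treat, without regard to intervention adherence". The primary outcome is percent weight loss from before to after the intervention. Arm is the main independent variable, in a general linear mixed model that allows for clustering.
- **Sensitivity analyses to determine the impact of key assumptions:** imputation methods under MCAR, MAR and MNAR are to be compared "in order to determine which underlying mechanism best fits our data".
- **Plans to address missing data:** "We will compare the results of the analysis using three approaches as a comprehensive sensitivity check". The three are PROC MIXED on available data (labelled MCAR), 25 multiple imputations under MAR, and pattern-mixture imputation under MNAR. The section then commits to monotone regression imputation of the outcomes, pooled in PROC MIANALYZE. On predictors it says: "We will use demographic covariates and prior weight measurements that are available in this predictive model". On purpose it says: "These imputations will help minimize loss of power resulting from attrition".

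**The concern.** There are three linked difficulties.

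1. The stated aim of the comparison cannot be met. MAR and MNAR differ in how the unseen outcomes are distributed given what was seen, and the data hold no information on that.
2. The analysis that gives the primary estimate is not fully pinned down. Two imputation analyses are planned under different assumptions, and both are described as part of a sensitivity check. This leaves room to choose between them after the results are known.
3. Arm is not among the named imputation predictors. For the post-intervention outcome, the only earlier study weight was taken before the intervention, so it carries no treatment effect. A programmer who follows the list would draw missing outcomes in both arms around one common mean. That would pull the estimated difference toward zero and work against the plan's own purpose for imputing.

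**Working it through.** **Step 1. What the comparison can show.** Any MNAR model can be matched by a MAR model that fits the observed data equally well, because the two differ only in the distribution of the missing values. MCAR against MAR can be partly checked, for example by comparing baseline data of those with and without a later weight. MAR against MNAR cannot. Agreement or disagreement among the three analyses measures sensitivity to the assumption, not fit.

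**Step 2. Reproduce the plan's power.** Inputs from the power section: difference 2.5 kg, SD 7, ICC 0.01, 16 churches of 12 per arm (192 per arm), two-sided 0.05.

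- Design effect = 1 + (12 − 1) × 0.01 = 1.11
- Effective n per arm = 192 / 1.11 = 173.0
- SE = 7 × √(2 / 173.0) = 0.753 kg, and 2.5 / 0.753 = 3.32
- Power = Φ(3.32 − 1.96) = 91.3%. Noncentral t gives 91.2% on 382 df and 89.5% on 30 df.

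The stated 91% reproduces.

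**Step 3. Shrinkage if arm is not a predictor.** Let a fraction f be missing in each arm and m be the common mean of the imputed values. Each arm's completed mean is (1 − f) × (its own mean) + f × m. The m terms cancel in the difference, leaving (1 − f) × 2.5 kg:

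- f = 0.05: 2.375 kg
- f = 0.10: 2.25 kg
- f = 0.20: 2.00 kg
- f = 0.30: 1.75 kg

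With unequal missingness of 30% and 10%, the same reasoning gives a factor of 0.7875, or 1.97 kg. Percent weight loss shrinks in the same proportion.

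**Step 4. Effect on power, by simulation.** The plan's inputs were used, with 4,000 runs per setting. Assumptions: one baseline covariate with correlation 0.2 to weight change; missingness depending on that covariate only and equal in both arms; 25 regression imputations; a church-mean t-test on 30 df; and Rubin's rules with small-sample df. The mixed model was a random-intercept REML fit to available data (2,000 runs).

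| Missing (assumed) | Arm not a predictor: difference, power | Arm a predictor: difference, power | Imputed by arm: power | Mixed model, available data: power |
|---|---|---|---|---|
| 5% | 2.36 kg, 85% | 2.49 kg, 87% | 87% | 90% |
| 10% | 2.23 kg, 81% | 2.48 kg, 87% | 87% | 88% |
| 20% | 2.00 kg, 69% | 2.50 kg, 83% | 83% | 84% |
| 30% | 1.74 kg, 50% | 2.48 kg, 77% | 76% | 77% |

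Simulation error is about 0.5 to 1 point. A second simulation (1,500 runs, missingness unrelated to any covariate) agreed. At 10, 20 and 30% missing it gave 2.26, 2.01 and 1.74 kg with power 81, 69 and 52% without arm. With arm, power was 87, 84 and 78%.

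**Step 5. Direction of the error.** With no true effect, rejection without arm was 4.4, 3.3, 1.5 and 0.7% at 5, 10, 20 and 30% missing. With arm it was 5.0, 4.9, 4.6 and 4.5%. Leaving arm out can hide a difference; it does not create one.

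**Step 6. Church in the imputation model.** Church is nested in arm, so church entered as ordinary regression terms keeps the difference near 2.5 kg. At ICC 0.01 it costs power: 71% at 20% missing and 56.5% at 30%. Imputing with arm but ignoring church, at 30% missing, gave null rejection in two simulations (2,000 and 1,000 runs) of 4.1 and 5.1% at ICC 0.01, 5.8 and 5.3% at 0.05, and 6.7 and 7.6% at 0.10. Ignoring church is therefore safe only near the planning ICC.

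**The case against.** The case on the other side is substantial, and most of it limits the point rather than removing it.

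- **The predictor list is not said to be complete.** The plan makes arm its main independent variable, and including it in the imputation may simply be unwritten. That stands. A reader might infer that the plan excludes arm, but the text supports only that arm is not named. The shrinkage is conditional on running the list as written.
- **The missing fraction is assumed.** The plan provides for recontact, REDCap monitoring, follow-up after dropout, and a window of nine weeks either side of each data collection date. Missingness could be low, and at 5% the loss is 2 to 3 points. That stands. A reader might infer that the trial has about 50% power, but that figure needs 30% missing and imputation without arm.
- **The plan does lean to an approach.** It says missing data will be imputed for the intention-to-treat analysis, commits to monotone regression imputation, and names a mixed model for the outcome. That stands. What is open is mainly whether the MAR or the MNAR imputation is primary.
- **The best-fit sentence sits under sensitivity analyses.** A reader might infer that the primary estimate will be picked after the results are seen. The plan does not say so; it only leaves room for it.
- **Pattern-mixture imputation need not use a numerical shift.** It can borrow from a reference pattern. That stands: the gap is that its assumption is unspecified, not that a shift size is missing.

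None of this rescues the aim of finding which mechanism fits, and a programmer working from the named predictors would leave arm out.

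**Conclusion.** The point holds in three parts, with different degrees of certainty.

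1. It is certain that the comparison cannot identify MAR or MNAR as the true mechanism.
2. The primary analysis is under-specified: imputation is favoured, but its assumption is not fixed.
3. The shrinkage is conditional on arm being left out. It affects the two imputation analyses for the post-intervention outcome. It does not affect the PROC MIXED analysis, whose model contains arm. So whether the primary result is attenuated depends on the choice left open in part 2.

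The power lost by omitting arm is 2 to 3 points at 5% missing, 5 to 6 at 10%, 14 at 20% and 27 at 30%. These figures rest on the plan's 2.5 kg, SD 7 and ICC 0.01, and on assumed equal missingness that depends on baseline only. They do not point to a sample-size error, since the stated 91% for complete data reproduces. Nor do they point to a raised risk of a false positive from leaving arm out.

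**What to change.** - Delete the best-fit clause and describe the three-way comparison as sensitivity to the missing-data assumption only.
- Before weights are analysed by arm, name one MAR analysis as primary. One option is the planned multiple imputation with arm added as a predictor, or run separately by arm. The other is the mixed model on available data. If the mixed model is chosen, describe it as valid under MAR rather than MCAR, and reword the sentence in the power section that relies on imputation to bring in all randomized participants.
- Keep the pattern-mixture analysis as sensitivity only, with its assumption (a reference pattern or a shift) set in advance.
- Give no blanket instruction on church. If the observed ICC is clearly above 0.01, prefer the mixed model on available data or an imputation with a random church effect to one that ignores church.

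The cost is SAP wording plus one predictor, or a by-arm run, in a step already planned. It needs no new data and no change in N.

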All study information and consent materials will be provided in English and/or Marshallese based upon the participants' preferences. Eligible participants will be provided a copy of the consent to review, and participants will have the opportunity to ask questions, consent, and enroll in the study. The consent process will include providing information to the potential participants and the opportunity to have bilingual Marshallese staff answer questions regarding study participation. The consent document will be given to the participant, and the informed consent process will be documented in the participant's research record. The consent document will be reviewed with the group and questions will be answered by research staff. An opportunity will be provided to all potential participants for individual, private discussion of the study and the consent document before they sign the consent. All members of the research team will be trained and certified in participant consent procedures, the study protocol, human subjects protection, and HIPAA regulations. After the consent process, a participant contact information form will be completed.

Data collection: Biometric and survey data will be collected during pre-intervention, post-intervention, and 12-month post-initiation events (which is 12 months from study initiation and six months after the first post-event data collection). The data collection window is up to nine weeks on each side of the data collection date to accommodate participant availability. The 12-month post-initiation event can be split into two data collection events. One for survey data collection using remote data collection methods and one for biometric data collection. In the event missing data is identified, participants will be contacted to collect the missing data.

Participants may be invited to participate in a qualitative interview to understand participants' perceptions of the intervention and implementation process. Participants may refuse any data collection or any questions within a data collection event.

Data Collection Instruments and Procedures

Biometric Data

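### As written, a missing post-intervention weight is imputed from demographics and earlier weights only, so a measured 12-month weight does not inform the imputed primary outcome

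*Combined protocol and SAP*

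**What the plan says.** **Follow-up.** Under Plans to address missing data: "The study team will continue to collect information on all outcomes from participants, unless consent is withdrawn". The Data collection paragraph adds: "Participants may refuse any data collection or any questions within a data collection event". Weight is measured before the intervention, after it and 12 months after initiation. The eligibility screener also records a weight.

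**Outcome and models.** The Statistical analysis plan makes percent weight loss from pre- to post-intervention the primary outcome. It fits the post-intervention and 12-month results in different models. A repeated-measures model with intervention, time and their interaction is assigned to the 12-month result.

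**Imputation.** Plans to address missing data lists three approaches to be compared: a random effects model in PROC MIXED, 25 multiple imputations in PROC MI under MAR, and pattern-mixture imputation under MNAR. It then specifies the imputation: "we will use monotone regression-based, multiple random imputations of the outcomes". The predictors follow: "We will use demographic covariates and prior weight measurements that are available in this predictive model".

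**Reliance on imputation.** The power section includes every randomized participant in the intention-to-treat analysis on the ground that missing data will be imputed.

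**The concern.** The follow-up rules allow a participant to miss the post-intervention weigh-in and be weighed at 12 months. For that person, the weights that precede the missing one are the screening and pre-intervention weights. The imputation text names no later weight. The missing value is therefore drawn as if the person had done as well as attenders with the same starting weight and demographics, although a weight taken about six months later is on file.

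Among people who missed the primary visit, that later weight is the most direct evidence of how they fared. Leaving it out gives up precision. If absence goes with poor weight loss, and does so more strongly in one arm, it also leaves in the PILI-WORD difference some bias that data already collected could reduce. The plan does not say how a gap followed by a return is to be handled, so the choice could be made after the data have been seen.

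**Working it through.** **1. The plan's own figure.** Inputs from the power section: 16 churches per arm, 12 people each (192 per arm, N = 384), difference 2.5 kg, SD 7 kg, ICC 0.01, two-sided 5% level. The plan states: "This achieves 91% power to detect a difference of 2.5kg between the group means".
- Design effect = 1 + (12 - 1) × 0.01 = 1.11.
- Effective n per arm = 192 / 1.11 = 173.0.
- Normal-approximation power = 0.913. With a noncentral t it is 0.912 on 382 df and 0.895 on 30 df.

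The 91% reproduces. It assumes a weight from all 384 participants.

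**2. Which weights reach the imputed primary outcome.**

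| Route | Does the 12-month weight enter? |
|---|---|
| Imputation text | No; demographics and earlier weights only |
| Post-intervention model | No; fitted separately from 12 months |
| PROC MIXED approach | Only if both visits are fitted jointly; not stated |
| Repeated-measures model | Possibly, but it is assigned to the 12-month result |

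**3. Precision.** The documents give neither a missed-visit rate nor a between-visit correlation, so these ranges are assumptions. Let m be the share missing the post-intervention weigh-in, q the share of those weighed at 12 months, and r the correlation of the two weight changes. The information recovered by using the later weight is about 384 × m × q × r².
- Low: 384 × 0.10 × 0.30 × 0.36 = 4.1 participants.
- Central: 384 × 0.15 × 0.50 × 0.49 = 14.1.
- High: 384 × 0.20 × 0.50 × 0.64 = 24.6.

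For power, take 384 × (1 - m) participants without the later weight, add the recovered number, and divide by 2 × 1.11 for the effective n per arm.

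| Case | Without | With | Gain in power |
|---|---|---|---|
| Low | 345.6: 0.883 | 349.7: 0.887 | about 0.4 points |
| Central | 326.4: 0.865 | 340.5: 0.878 | about 1.4 points |
| High | 307.2: 0.844 | 331.8: 0.870 | about 2.6 points |

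**4. Bias, absence driven by the unseen post-intervention loss.** Large-sample simulation, all settings assumed: mean losses 2.0 and 4.5 kg (true difference 2.5), SD 7, about 13-14% absent, absence linked to poor loss more strongly in one arm.
- Imputing without the 12-month weight gives about 2.9 kg, an excess of about 0.4 kg.
- With 30-50% of absentees returning and r of 0.6-0.8, adding the 12-month weight removes about 10-31% of the excess. That is 0.10 × 0.4 = 0.04 kg to 0.31 × 0.4 = 0.12 kg. This run used log-odds of absence of 0.6 and 0.2 per SD in the two arms.
- With 50-80% returning, about 17-51% is removed.

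**5. Bias, most favourable case for the fix.** Here absence in one arm depends only on the 12-month change (log-odds 1 per SD), and every absentee is weighed at 12 months. Without the later weight that arm's mean shifts by about 0.2-0.3 kg at 5% absent, 0.3-0.6 kg at 10% and 0.6-1.1 kg at 20%. With it the shift is about zero. This is a ceiling on what the change could achieve, not an expectation.

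**The case against.** **Other analyses are planned.** The PROC MIXED approach is meant to use every available observation, and pattern-mixture imputation addresses informative absence. None of the three approaches is named as primary. A reader might infer that the 12-month weight is ignored in every analysis of the primary outcome. The documents do not establish that, because a joint fit of both visits would use it. The plan does not commit to a joint fit, however, and the separate modelling of the two visits points the other way.

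**The follow-up is not wasted.** A reader might infer that the imputation rule contradicts the follow-up rule, or that the later weights cannot be used. That goes too far: the 12-month weight is itself a modelled outcome.

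**The method need not fail.** A reader might infer that gaps followed by a return break monotone regression outright. If only the post-intervention outcome is imputed, from complete predictors, that dataset is monotone and the method runs. If all visits are imputed together, intermittent gaps can first be filled by MCMC, which the text does not exclude. It does not provide for that step either.

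**The pattern may be uncommon.** Each visit has a window of up to nine weeks either side, missing data are chased, and people planning to move within six months are excluded. These steps reduce the pattern but cannot remove it while refusal is allowed.

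**The effect is modest and assumed.** This stands. Where absence depends on the unseen post-intervention weight, the later weight removes only part of the bias, and the rest is the pattern-mixture analysis's task.

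**Conclusion.** The point holds in a limited form. The plan states a method, and that method, followed as written, imputes a missing post-intervention weight without a 12-month weight that the plan expects to collect. The separate post-intervention model does not repair this, and the mixed model does so only under a joint fit that is not specified.

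The textual gap is clear; its size is not. Under the assumed ranges (10-20% absent, 30-50% of them returning, correlation 0.6-0.8) the information forgone is that of about 4 to 25 of 384 participants, or roughly 0.4 to 2.6 points of power. In the step 4 scenario with the same return rates and correlations, the avoidable bias is about 0.04-0.12 kg against a 2.5 kg target. It could be larger if more absentees return, and is negligible if few do. A reader might infer that the primary comparison is seriously biased or that using the later weight would cure any bias; the documents support neither. The change is worth making because it is cheap and uses data already planned.

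**What to change.** In Plans to address missing data:
- Replace monotone regression with a method for arbitrary missing patterns (PROC MI with FCS or MCMC). Apply it to the whole dataset, run it within arm, and state how church clustering is accounted for. Use one method throughout: PROC MI applies its method to a dataset, so reserving monotone regression for some participants is not workable in a single run.
- Replace the restriction to earlier weights with all available weights: screening, pre-intervention, post-intervention and 12-month. Keep the demographic covariates.
- Keep the pattern-mixture analysis for absence that depends on unseen weights.

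Alternatively, state that the post-intervention contrast is estimated from a joint repeated-measures model of both visits.

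Either change should be settled before outcome data are examined. The cost is SAP wording and minor SAS code, with no new data. The one real downside is that the final imputed primary result must wait for the 12-month weights.
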